9.3.2 Follow-up of pregnancy

Additional information on the pregnancy and its outcome will be collected using the Sobi Pregnancy Notification Form and reported to the Sponsor.

Any AE associated with the pregnancy must be reported in the AE pages of the eCRF. Any SAE occurring during the pregnancy must be reported on an SAE form as described in section 9.2.2.

9.4 Study safety monitoring

Clinical study safety information (e.g. AEs, SAEs, infection AEs, infusion related reactions, laboratory values, ECGs and vital signs) is monitored and reviewed on a continuous basis by the Sponsor's Clinical team (in charge of ensuring subjects' safety as well as data quality) by periodically monitoring clinical

studies activities from protocol conception to database closure. In addition, an IDMC is monitoring safety data (see section 3.6.1).

10 BENEFIT/RISK MANAGEMENT

10.1 Potential benefits

Data collected to date in HLH patients undergoing HSCT (Studies NI-0501-04/05 and compassionate use) and published data (6) from patients with various underlying diseases receiving HSCT, support the potential use of emapalumab to preempt GF by neutralizing IFN γ production and consequently prevent the loss of the graft.

Currently, once GF is confirmed, the only treatment is a second transplant.

Based upon the rates of overall survival, GF following HSCT is a life-threatening condition. The one year overall survival after GF has been reported between 45 to 60%, regardless of the procedure performed after GF is confirmed. Although loss of the graft itself leads to death only in a minority of cases (less than 5%) (14, 15), the risk of death in the absence of a second HSCT is almost certain, mostly due to infections in the context of extended neutropenia (16). The chances of survival depend on the quality of the graft, the initial successful engraftment, the mismatch between the donor and recipient and on the conditioning regimen. Nevertheless, even after a second transplant, survival remains low with approximately 1 out of 2 patients alive after one year, for the most optimistic reports.

There is significant unmet medical need for the prevention and/or treatment of GF. The availability of a therapeutic option which would lower the risk of GF in high risk patients would:

- Reduce the number of patients who would require a potential second HSCT.
- Provide an opportunity to lower GvHD occurrence by allowing an increased use of T-cell depleted grafts or stronger immunosuppression in a context where anti- IFN γ would promote engraftment.
- Improve the chance of success in fragile patients due to disease or age with less toxic conditioning regimens.
- Ultimately, reduce the mortality post-HSCT.

Patients that will not receive emapalumab and included in the study, will benefit from medical monitoring of their post-transplant clinical intercourse for up to 3 years. These patients will also contribute to further assess the relevance of CXCL9 as a potential biomarker to predict the risk of GF.

10.2 Potential risks

Due to the nature of emapalumab chemical structure and mechanisms of action and based on current experience with emapalumab, the following potential risks have been identified: infections caused by pathogens likely favoured by the lack of IFN γ biological activity, IRRs, and occurrence of anti-emapalumab antibodies.

In addition, based on literature evidence and mechanisms of action of emapalumab, IFN γ neutralization may adversely affect graft-versus-tumor activity after allo-HSCT.

10.2.1 Infections

The impact on the immune defense caused by the neutralization of IFN γ is known from patients with inborn errors of the IL 12/23-IFN- γ circuit, particularly patients with complete or partial IFN γ receptor deficiency, and patients developing neutralizing auto anti-IFN γ antibodies. Patients with IFN γ R deficiency are prone to develop mycobacterial infections and, although to a lesser extent, Salmonella infections (17, 18). The mean age of the first environmental mycobacterial infection is 3.1 and 13.4 years in patients with complete and partial deficiency, respectively (19).

No systematic prophylaxis is recommended in these patients. If an infection occurs, appropriate antibiotic therapy based on sensitivity of isolated species is prescribed.

Individuals with anti-IFN γ auto-antibodies are also susceptible to develop mycobacterial infections (for the vast majority atypical mycobacterial infections), but also opportunistic infections (e.g., caused by *Histoplasma Capsulatum*, *Salmonella*, Herpes Zoster virus) (20).

Toxicological studies carried out with emapalumab have shown an increased susceptibility to enteral pathogen infections in monkeys having received emapalumab, when the enteral pathogen was present in the intestinal tract prior to emapalumab administration. Therefore, presence of infections due to *Shigella*, *Salmonella* and *Campylobacter* pathogens is part of the exclusion criteria.

As to the development of infections caused by pathogens known to be favored by the absence of IFN γ biological activity, a reactivation of Herpes Zoster virus (HZV) (which resolved after a normal course with no sequelae) was observed in one healthy volunteer, at a dose of 3 mg/kg; and one HLH patient enrolled in the NI-0501-04 study developed a disseminated histoplasmosis which resulted in treatment discontinuation. This infection resolved with adequate antifungal therapy, even if emapalumab was still at detectable concentrations in blood.

Other infections reported during or after administration of emapalumab are the same ones commonly observed in immunocompromised patients or are the same ones described in pediatric populations (seasonal viral infections). Patients with active infections (except for the exclusionary ones) were enrolled and treated in the study. The presence of active infections did not lead to the discontinuation or dose decrease of emapalumab treatment, and infections resolved on study drug when treated appropriately and not associated with a refractory disease status. Severe or serious infections were generally reported in patients with previous recent significant exposure to immunosuppressive treatments as they added an additional risk factor for infection development. Importantly, emapalumab treatment has not been associated with myelosuppression.

For more information regarding the risk of infections in completed and ongoing clinical trials with emapalumab, refer to the latest version of the IB.

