EXCLUSION CRITERIA	
 1. Pregnant (or planning to become pregnant) or lactating female patients. 2. Body weight < 3 kg. 3. Underlying malignant disease with Karnofsky/Lansky performance status equal or less than 40 or an Eastern Cooperative Oncology Group (ECOG) performance status equal or less than 3. 4. Patients presenting CXCL9 levels 10 times above the upper limit of the 95% interval (CI) of the normal range (reported in the CXCL9 assay laboratory manual) within 24 hours prior to HSCT. 5. Clinically manifested infections caused by typical and atypical Mycobacteria, Salmonella, Histoplasma capsulatum and Herpes Zoster on the day of HSCT. 6. Active or clinical suspicion of latent tuberculosis. 7. Concomitant diseases that in the opinion of the Investigator may interfere with the assessment of emapalumab safety or efficacy. 8. Receipt of a Bacille Calmette-Guerin (BCG) vaccine within 3 months prior to HSCT. 9. Receipt of a live or attenuated live (other than BCG) vaccine within 6 weeks prior to HSCT. 10. Current or scheduled administration of therapies known to potentially trigger a cytokine release syndrome within 21 days from HSCT. 11. Patients having received IFNγ during the last 2 weeks prior to HSCT and/or who require treatment with IFNγ. 12. Patients having received emapalumab during the last 6 months prior to HSCT, unless it is known that emapalumab is no longer detectable.

	
13. Patients having received kinase inhibitors (Janus kinase inhibitors [JAKi] or bruton tyrosine kinase inhibitors [BTKi]) one week (or 5 half-lives whichever is greater) prior to HSCT.
 
14. Intolerance to antimicrobial and virus infection prophylaxis.
 
15. Hypersensitivity to emapalumab or any of the excipients.
 
16. Ongoing participation in an interventional trial or administration of any investigational drug (within 3 half-lives of the investigational drug) with the exception of interventional trials involving supportive care such as probiotics or antiemetics, graft manipulation, or use of new combinations or new dosing of conventional therapies for conditioning and prophylaxis pre-HSCT.

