	
 • If CXCL9 is measured above threshold and there are signs of sGF (i.e. donor chimerism drop of at least 10% for 2 consecutive measurements and/or ANC below 500 cells/μL and/or thrombocytopenia below 30000/μL not explained by any other reason than potential graft rejection), patients may optionally enter the treatment period, if the investigator will consider pre-emptive treatment with emapalumab the best option for the patient. • If CXCL9 is measured below threshold, patients will continue the extended monitoring period until Day 98\pm3 days or until a second HSCT is planned. 
Criteria not to start treatment during monitoring or extended monitoring
 
Patients presenting the following conditions at time of initiation of emapalumab treatment will not be eligible to receive emapalumab and will move to the phone-call follow-up period for non-emapalumab treated patients.
 
 • Uncontrolled infections (defined as clinically active infection regardless of treatment). • Clinical manifestations of infections representing exclusion criteria (i.e. Atypical mycobacteria, Salmonella, Histoplasma capsulatum, Herpes zoster). • Re-occurrence or progression of the underlying malignant disease based on medical judgment. • Graft versus host disease (GvHD). 
Treatment period
 
 • Patients will be monitored for eligibility to treatment during the monitoring and extended monitoring periods. Patients treated for primary or secondary GF will receive emapalumab for maximum 15 infusions or until engraftment is confirmed. • Engraftment is defined as ANC \geq 500 cells/μL for 3 consecutive measures and donor chimerism above 60% (for primary GF) or ANC \geq 500 cells/μL for 3 consecutive measures and 2 consecutive measures of donor chimerism above 60% or 7 days of platelets above 20000 cells/μL without transfusion (for secondary GF). • Preferably, ANC recovery should be based upon three consecutive laboratory values (ANC sample drawn 1 or 2 days apart maximum). • Patients must be hospitalized in case of active infections requiring intravenous (IV) antimicrobial therapy during treatment. • If engraftment is confirmed prior to the last dosing day (dose 15) or if the patient discontinues treatment, patients will perform all assessments as per end of treatment visit (EoT) and can be discharged if hospitalized provided that there is no active infections requiring IV antimicrobial therapy. • Patients who take prohibited medications will not be discontinued from emapalumab treatment unless for medical reasons. • Pre-emptive treatment for secondary GF is optional and it is investigator's responsibility to decide whether to start pre-emptive treatment with emapalumab or not.

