1.2.2.2 Toxicology

Binding and functional data demonstrated that Rhesus and Cynomolgus monkeys were relevant species for evaluating the safety of emapalumab. No off-target toxicity was attributed to emapalumab when it was administered to Cynomolgus monkeys in 13 weekly doses of up to 200 mg/kg. Shigella and Campylobacter infections were observed at all dose levels (10 to 200 mg/kg/week) in animals originally harboring gastrointestinal pathogens (Shigella, Salmonella, Campylobacter) prior to emapalumab administration. These findings were assessed to be in line with the expected pharmacological effect of emapalumab (i.e. neutralization of IFN γ), given the role played by IFN γ in controlling these pathogens. Subsequently, in a study where Cynomolgus monkeys were free from gastrointestinal pathogens at screening, weekly administrations of emapalumab for 8 consecutive weeks at doses up to 30 mg/kg were well tolerated with no toxicity or gastrointestinal disturbances observed and no need for antibiotic prophylaxis.

While it was not possible to establish the No Observed Adverse Effect Level (NOAEL) in the 13-week toxicity study, the NOAEL in the 8-week study was assumed to be the highest dose tested, i.e. 30 mg/kg/week.

Embryo-fetal development, as well as fertility and early embryonic development studies, were performed in mice, testing therapeutic and multiple doses of the rat anti-mouse IFN γ surrogate antibody XMG 1.2. No effects on embryo-fetal development (i.e., embryo-fetal survival, fetal weight, sex ratio or morphology) were observed. No effects were observed on estrous cycling in treated females, mating or fertility in treated male or treated female mice, male reproductive organ weights, or any ovarian, uterine, or litter parameter related to treatment of male or female mice. The NOAEL for emapalumab in these studies was therefore determined to be the highest dose-level tested of 150 mg/kg.

More details are available in the current Investigator's Brochure (IB).

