3.4.2 Allogeneic HSCT

Assessments to be performed on the day of HSCT are presented in the schedule of assessment (Table 5a and Table 5b) Patient's eligibility is assessed by checking inclusion/exclusion criteria prior to HSCT on Day 0. A patient is considered included in the study if he/she meets all inclusion/exclusion criteria prior to HSCT.

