- If CXCL9 is measured below threshold, patients will continue the extended monitoring period until Day 98 \pm 3 days or until a second HSCT is planned.

Criteria not to start treatment during monitoring or extended monitoring

Patients presenting the following conditions at time of initiation of emapalumab treatment will not be eligible to receive emapalumab and will move to the phone-call follow-up period for non-emapalumab treated patients (see section 3.4.5).

- Uncontrolled infections (defined as clinically active infection regardless of treatment).
- Clinical manifestations of infections representing exclusion criteria (i.e. Atypical mycobacteria, Salmonella, Histoplasma capsulatum, Herpes zoster).
- Re-occurrence or progression of the underlying malignant disease based on medical judgment.
- GvHD.

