4.2 Exclusion criteria

1. Pregnant (or planning to become pregnant) or lactating, female patients.
2. Body weight < 3 kg.
3. Underlying malignant disease with Karnofsky/Lansky performance status equal or less than 40 or an ECOG performance status equal or less than 3.
4. Patients presenting CXCL9 levels 10 times above the upper limit of the 95% CI of the normal range (reported in the CXCL9 assay laboratory manual) within 24 hours prior to HSCT.
5. Clinically manifested infections caused by typical and atypical Mycobacteria, Salmonella, Histoplasma capsulatum and Herpes Zoster on the day of HSCT.
6. Active or clinical suspicion of latent tuberculosis.
7. Concomitant diseases that, in the opinion of the Investigator, may interfere with the assessment of emapalumab safety or efficacy.

8. Receipt of a Bacille Calmette-Guerin (BCG) vaccine within 3 months prior to HSCT.
9. Receipt of a live or attenuated live (other than BCG) vaccine within 6 weeks prior to HSCT.
10. Current or scheduled administration of therapies known to potentially trigger a cytokine release syndrome within 21 days from HSCT.
11. Patients having received IFN γ during the last 2 weeks prior to HSCT and/or who require treatment with IFN γ .
12. Patients having received emapalumab during the last 6 months prior to HSCT, unless it is known that emapalumab is no longer detectable.
13. Patients having received kinase inhibitors (Janus kinase inhibitors [JAKi] or bruton tyrosine kinase inhibitors [BTKi]) one week (or 5 half-lives whichever is greater) prior to HSCT.
14. Intolerance to antimicrobial and viral infection prophylaxis.
15. Hypersensitivity to emapalumab or any of the excipients.
16. Ongoing participation in an interventional trial or administration of any investigational drug (within 3 half-lives of the investigational drug) with the exception of interventional trials involving supportive care such as probiotics or antiemetics, graft manipulation, or use of new combinations or new dosing of conventional therapies for conditioning and prophylaxis pre-HSCT.

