	Urinalysis	X			
	Coagulation	X			
	Biochemistry ⁴	X			
	Hematology including differential hematology ⁴	X			X
	Absolute Neutrophil Count (ANC)		X ⁵	X	
	Donor chimerism ⁶			MD1, MD7, MD15, MD21, MD27, MD33, MD39	X
	HLA antibodies against donor cells		X		
CXCL9 ⁸		X ⁵	X		
Inflammatory biomarkers ⁷	X	X	X		
AEs & Concomitant medications	X	X	X		

Table 5a foot notes
Abbreviations: SD: Screening Day; MD: Monitoring Day; D: Day; EM: Extended Monitoring; BP: Blood Pressure; HR: Heart Rate; TB: Tuberculosis; ANC: Absolute Neutrophil Count; HLA: Human Leukocyte Antigen; CXCL9: C-X-C Motif Chemokine Ligand 9; AEs: Adverse Events
1: All assessments/procedures must be performed pre HSCT, unless otherwise specified
2: TB results from the screening (IFN γ -release assay/PPD test) must be available at the latest prior to HSCT for eligibility assessment.
3: Atypical mycobacteria, salmonella, histoplasma capsulatum, herpes zoster, HHV6, CMV, EBV, adenovirus, parvovirus.
4: Biochemistry: Glucose, C-reactive protein (CRP), Sodium, Potassium, Chloride, Calcium, Magnesium and Phosphate, AST, ALT, γ GT, ALP, LDH, bilirubin (total, direct and indirect), triglycerides, cholesterol (total and HDL), Albumin, creatinine, urea (fast conditions whenever possible), Ferritin. Hematology: hematocrit, hemoglobin, platelets, RBC, WBC. Hematology differential: lymphocytes, monocytes, neutrophils.
5: Pre HSCT
6: Donor chimerism must be assessed at the monitoring visits as indicated unless the patient transitioned to extended monitoring period or treatment
7: Free IFN γ , CXCL9 and other inflammatory biomarkers in serum (e.g. IL-6, TNF α , sCD163 and sIL2R α). These samples may also be used to assess baseline values of ADA.
8: The CXCL9 sample is analysed locally with a device provided by the Sponsor.

Table 5b: Schedule of assessments for Screening, HSCT, monitoring and extended monitoring (cohort 1, 2 and 3) – Patient weight < 30 kg

PERIOD (Duration)	SCREENING (Up to 13 days)	HSCT ¹ (1 day)	MONITORING (Up to 42 ±1 days)	EXTENDED MONITORING (Up to 98 ±3 days)	
VISITS Days ± visit window	SD -21 to SD-8	D0	MD1, MD2, MD3, MD4, MD5, MD6, MD7 MD9, MD11, MD13, MD15, MD17, MD19, MD21, MD24±1, MD27±1, MD30±1, MD33±1, MD36±1, MD39±1, MD42 ±1	Visits every 7±1 days First EM visit is 7±1 days from the last day in the monitoring period (patient transition to EM period as soon as ANC ≥500 in the monitoring)	
Demographics and baseline characteristics	Informed Consent	X			
	Demographics	X			

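### Section 10.2.1 says Shigella and Campylobacter infections are excluded, but no list governing eligibility or treatment start names either; the residual gap is small

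*Combined protocol and SAP*

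**What the plan says.** Section 10.2.1 (Infections) reports that monkeys given emapalumab were more susceptible to enteric infection when the pathogen was already in the gut, and concludes: "Therefore, presence of infections due to *Shigella*, *Salmonella* and *Campylobacter* pathogens is part of the exclusion criteria". The source is Section 1.2.2.2 (Toxicology): "Shigella and Campylobacter infections were observed at all dose levels (10 to 200 mg/kg/week) in animals originally harboring gastrointestinal pathogens".

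Exclusion criterion 5, worded identically in the synopsis and in Section 4.2, reads: "Clinically manifested infections caused by typical and atypical Mycobacteria, Salmonella, Histoplasma capsulatum and Herpes Zoster on the day of HSCT". None of the other 15 criteria names an enteric pathogen. The nearest is criterion 7: "Concomitant diseases that, in the opinion of the Investigator, may interfere with the assessment of emapalumab safety or efficacy".

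Section 3.4.2 applies the written criteria before transplant on Day 0: "A patient is considered included in the study if he/she meets all inclusion/exclusion criteria prior to HSCT".

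Two of the conditions that bar the start of emapalumab (synopsis and Section 3.4.3) matter here. One is named: "Clinical manifestations of infections representing exclusion criteria (i.e. Atypical mycobacteria, Salmonella, Histoplasma capsulatum, Herpes zoster". The other is general: "Uncontrolled infections (defined as clinically active infection regardless of treatment".

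**The concern.** Section 10.2.1 tells the reader that a specific safety exclusion exists, and the criteria that sites apply do not contain it for two of the three pathogens. The two left out are the ones that the toxicology summary reports as having caused infections in dosed animals. Salmonella, which is named, appears in that summary only among the organisms that the animals carried.

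Two things are at stake. The first is accuracy: an ethics committee or IDMC member who relies on 10.2.1 would credit the protocol with an exclusion that investigators are not told to apply, and Section 10.2.5 puts strict exclusion criteria first among its risk minimization measures. The second is eligibility: a patient with manifest Shigella or Campylobacter infection on Day 0 meets no named exclusion, whereas the same patient with Salmonella does.

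**Working it through.** No formula applies and the plan gives no figure to reproduce. The check sets the Section 10.2.1 sentence against every operative list in the protocol that names Salmonella.

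**Lists that decide eligibility or treatment start**

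| Place | Salmonella | Shigella | Campylobacter |
|---|---|---|---|
| Synopsis, exclusion criterion 5 | yes | no | no |
| Section 4.2, exclusion criterion 5 | yes | no | no |
| Synopsis, named bar to starting treatment | yes | no | no |
| Section 3.4.3, named bar to starting treatment | yes | no | no |
| Section 8.4.1, eligibility and do-not-treat text | yes | no | no |
| Section 10.2.5.1, measures before enrollment | yes | no | no |

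That is 6 lists, with Shigella in 0 of 6 and Campylobacter in 0 of 6. The named start bar introduces its list with an i.e., so it is a closed restatement of the exclusionary infections and leaves no room for unlisted ones.

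**Lists that only direct a search for infection**

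These are Tables 5a, 5b, 6a, 6b, 7a and 7b (6 lists) and Section 10.2.5.2 (1 list): 6 + 1 = 7. Shigella is in 0 of 7 and Campylobacter in 0 of 7. They are weaker evidence about exclusion. The footnote to Table 5a, for example, reads "Atypical mycobacteria, salmonella, histoplasma capsulatum, herpes zoster, HHV6, CMV, EBV, adenovirus, parvovirus", and the last five entries are not exclusionary.

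Together 6 + 7 = 13 lists name Salmonella and none names the other two. In the whole document Shigella and Campylobacter each occur three times: twice in Section 1.2.2.2 and once in Section 10.2.1.

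**What the omission lets through**

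1. Day 0, manifest Salmonella infection: excluded by criterion 5.
2. Day 0, manifest Shigella or Campylobacter infection: no named exclusion applies. Criterion 7 may keep the patient out, but only if the investigator judges that the disease would interfere with assessing the drug.
3. Infection still clinically active when the treatment criteria are met: dosing is barred by the general rule on uncontrolled infections, whatever the pathogen and whether or not it is being treated.
4. Infection clinically resolved by then: neither the general nor the named bar applies, and the patient can be dosed. Treatment can start at any time in a monitoring period of up to 42 days, or in extended monitoring up to day 98, so there is time for recovery. Such a patient may still carry the organism, which is the state that the toxicology summary describes in the animals before dosing.

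Only step 4 separates the protocol as written from the protocol as Section 10.2.1 describes it, so far as exposure to the drug is concerned.

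**The case against.** The strongest reply is that the operative text is clear and consistent. The six governing lists agree in omitting the two pathogens, and the outlier is one descriptive sentence in a risk section. That sentence misdescribes the criteria but does not alter them, and no investigator is handed two competing lists to apply. Inclusion on Day 0 exposes nobody to emapalumab. Section 12.1 expects only 10 to 30% of monitored patients to meet the criteria for primary graft failure treatment, and at that point the general infection rule protects against overt disease. Section 10.2.5.1, in the same chapter, gives a list that matches the actual criteria on this point. All of this stands, and it is why the point is minor. It does not make the sentence in 10.2.1 true. Criterion 7 is discretionary, and the general rule acts only at dosing.

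It is also fair to say that adding names to a criterion limited to clinically manifest infection will not find silent carriers. That is equally so for Salmonella today.

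Three stronger readings are tempting and should not be drawn:

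- A reader might infer that the protocol allows dosing during active Shigella or Campylobacter infection. Section 3.4.3 forbids it.
- A reader might count 13 eligibility lists in conflict with 10.2.1. Seven of the 13 are search lists, and the 13 already include both printings of criterion 5.
- A reader might conclude that the benefit-risk statement in Section 10.2.6 fails. It refers to the measures in place in the protocol, and the exclusions set out just before it in 10.2.5.1 omit both pathogens.

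**Conclusion.** The inconsistency is real, and nothing in the documents resolves it. Section 10.2.1 states an exclusion for three enteric pathogens. The six lists that govern eligibility or treatment start carry it for one, and the seven search lists are no wider. The severity is minor. The residual gap is mainly a patient with manifest Shigella or Campylobacter infection on Day 0 who is included and clinically recovers before dosing.

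This rests on two readings: that sites apply the written criteria rather than the 10.2.1 sentence, and that a clinically recovered patient no longer counts as having an active infection under Section 3.4.3. The documents give no rate for either infection, so the number of patients concerned cannot be estimated. Endpoints, sample size and interim rules are untouched.

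**What to change.** Insert Shigella and Campylobacter beside Salmonella in exclusion criterion 5 (synopsis and Section 4.2). Make the same insertion in the named bar to starting treatment (synopsis and Section 3.4.3), in the eligibility and do-not-treat text of Section 8.4.1, and in Section 10.2.5.1. State in 8.4.1 that this creates no new mandatory test. The search lists in Tables 5a to 7b need not change.

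The cost is a wording amendment and the loss of any patient with manifest infection by either pathogen on Day 0, whom Section 10.2.1 already describes as excluded.

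If the sponsor does not intend this exclusion, correct the sentence in Section 10.2.1 to name Salmonella only. That changes one sentence and loses no patient, but it gives up the stated safeguard for the other two pathogens. The documents do not show which was intended, so the choice is the sponsor's.
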